TITLE OF STUDY: A Comparison of Surgical Conditions between Deep vs Moderate Neuromuscular Blockade with Rocuronium in patients undergoing Endolaryngeal Procedures

OBJECTIVES:

Primary Study Objective: To compare the proportion of patients with a score of excellent for surgical conditions of deep Neuromuscular Blockade (NMB) (TOF 0, PTC 1–2) versus moderate NMB (TOF 1–2) using Rocuronium in patients undergoing Endolaryngeal Procedures

Secondary Study Objective:

1. To describe the proportion of patients who are Ready to Discharge from operating room, in both the sugammadex 4 mg/kg after deep Neuromuscular Blockade (NMB) (TOF 0, PTC 1–2) group and sugammadex 2 mg/kg after moderate NMB (TOF 1–2) group .
2. To describe the proportion of patients who are Ready to Discharge from Post Anesthetic Care Unit (PACU), in both the sugammadex 4 mg/kg after deep Neuromuscular Blockade (NMB) (TOF 0, PTC 1–2) group and sugammadex 2 mg/kg after moderate NMB (TOF 1–2) group .
3. To assess frequency of clinical signs of early recovery during Endolaryngeal Procedures both deep NMB and Moderate NMB.
Clinical signs of early recovery:
 - a. Airway pressure alarm
 - b. Movement of Vocal cords on Laryngeal Video monitor
 - c. Movement of the abdomen
 - d. Change of End Tidal CO₂

STUDY DESIGN: Overview: A multi-center, open-label, assessor-blinded, randomized, parallel intervention trial.

Number of Study Centers: This study will be conducted at 6 centers throughout Thailand.

Duration of Participation: Each subject will participate in the study for approximately up to 1 day from the time the subject signs the Informed Consent Form (ICF) through the last data collection point. The subjects will be observed for the post-operative complication for 1 day after study drug cessation.

Duration of Study: The total study duration is 16 months (4 months of institutional review board submission/approval, 8 months of enrollment period, 3 months of study analysis and reporting)

Key Inclusion/Exclusion Criteria:

Inclusion criteria:

1. Male or female aged 18 – 60 years; ASA I-III.
2. Subjects have been planned for elective endolaryngeal Procedures (Direct Laryngoscopy with laser (micro-)surgery in patients with endolaryngeal lesions.

Exclusion criteria:

1. Any renal impairment (CrCL < 80 ml/ min)
2. Any hepatic impairment; Child Pugh A, B or C
3. BMI > 30 kg m²
4. Known or suspected generalized neuromuscular disorders

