We will describe the data distribution of each collected variable. We will characterize subjects in both groups by demographics, comorbidities, clinical characteristics i.e. neuromuscular weakness grading, and distribution of ASA Classification pattern. Categorical variables will be summarized by frequency and percent while continuous variables will be summarized by the mean, median, standard deviation, and range.

Clinical Outcomes:

The data analysis will be based on the intent-to-treat approach. Categorical variables will be compared using the Fisher's exact test while continuous variables will be compared using the student's t-test or Mann-Whitney U test, depending on the sample distribution.

The level of statistical significance for all analyses is set at 0.05. All comparisons will be made using an alpha level of 0.05.

Sample Size: By using 80% power and 1-sided $\alpha=0.05$, we performed sample size calculation for the proportional outcome. Based on data from the BLISS study¹², the proportion of patients with a score of Excellent on the Surgical Rating Score (SRS) among subjects who receive deep NMB with Rocuronium is approximately 99%, while this proportion for patients who received moderate NMB with atacurium followed by mivacurium was lower (82%). The calculated subjects is required 36 subjects per arm. Since we expect 13% of withdrawal from the study¹³, we need to inflate the total sample size to 80 subjects (40 subjects per arm)

Efficacy Analysis:

1. Primary Efficacy endpoints:

The Proportion of patients who have a surgical conditions score of excellent (total score = 8-9) will be compared between the Moderate NMB and Deep NMB groups.

2. Secondary outcome

- 1) The proportion of patients who are ready to be discharged from post- operative care, defined as Modified Aldrete's score ≥ 9 , at 0, 15, 30,60, 90 minutes after reach of TOF > 0.9 will be summarized.
- 2) The proportion of patients who are ready to be discharged from the operating room, defined as TOF > 0.9 at time of tracheal extubation, at 1, 3, 5, 10 minutes after finish of Procedures will be summarized.
- 3) The frequency of patients with clinical signs of early recovery during Endolaryngeal Procedures will be compared between the deep NMB and Moderate NMB arms.

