Safety Analysis: This is a post-marketing study of treatment outcomes associated with surgical conditions and readiness of discharge from Post-Operating Care Unit(PACU) with Rocuronium and Sugammadex. Responsibility for clinical follow-up resides with the prescribing physician. Therefore, reporting of AEs and SAEs as they occur in clinical practice should follow the established Procedures for approved, marketed drugs in compliance with applicable laws and regulations. This applies to AEs and SAEs noted by the prescribing physician through clinical observation, clinical monitoring, diagnostic Procedures or other applicable methods.

Interim Analysis: N/A

Section #3- Core Protocol

2.1.1 List the objectives.

1.1) Primary Efficacy Objective:

1. To compare the proportion of patients with a score of excellent for surgical conditions of deep Neuromuscular Blockade (NMB) (TOF 0, PTC 1–2) versus moderate NMB (TOF 1–2) using Rocuronium in patients undergoing Endolaryngeal Procedures.

Surgical Conditions will be rated using a four-point surgical condition scale by one dedicated Surgeon from each center.

- TOF = Train of Four
- PTC = post-tetanic counts

1.2) Secondary Objective:

1. To describe the proportion of patients who are Ready to Discharge from operating room, in both the sugammadex 4 mg/kg after deep Neuromuscular Blockade (NMB) (TOF 0, PTC 1–2) group and sugammadex 2 mg/kg after moderate NMB (TOF 1–2) group .

**Readiness to discharge:* Readiness to Discharge from operating room, which is defined by train of Four ratio > 0.9 at any time after finish of Procedures.

2. To describe the proportion of patients who are Ready to Discharge from PACU*, in both the sugammadex 4 mg/kg after deep Neuromuscular Blockade (NMB) (TOF 0, PTC 1–2) group and sugammadex 2 mg/kg after moderate NMB (TOF 1–2) group .

- **Readiness to discharge from PACU is defined below.*
 - Modified Aldrete's scoring system is used for determining when patients can be safely discharged from the postanesthesia care unit (PACU) to either the postsurgical ward or to the second stage (Phase II) recovery area.
 - Modified Aldrete's score: A score ≥ 9 is required for discharge.

3. To assess frequency of clinical signs of early recovery during Endolaryngeal Procedures both deep NMB and Moderate NMB..

Clinical signs of early recovery:

- a. Airway pressure alarm
- b. Movement of Vocal cords on Laryngeal Video monitor
- c. Movement of the abdomen
- d. Change of End Tidal CO₂

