Vocal cord 
 • Position • Movement 	
 • Abducted • None 	
 • Intermediated • moving 	
 • Closing 	
 • Closed
Reaction to insertion of the endoscopic tube and cuff inflation 
 • Diaphragmatic movement • coughing 	
 • None • None 	
 • Slight^β movement • None 	
 • Vigorous movement^θ • Sustained coughing^θ 	
 • Bucking • Severe coughing

‡Laryngoscopy

Easy: jaw relaxed, no resistance to blade insertion

Fair: jaw not fully relaxed, slight resistance to blade insertion

Difficult: poor jaw relaxation, active resistance of the patient to laryngoscopy.

β One to two weak contractions or movement for less than 5 s.

θ More than two contractions and/or movement for longer than 5 s.

Endolaryngeal surgical site conditions⁹:

Excellent ;Score = 8-9

Good ;Score = 6 -7

Fair ;Score = 3-5

Poor ;Score =0-2

Surgical rating

During the laryngoscopic Procedures, the surgical condition is scored by the surgeon using a four-point SRS right after the Procedures. To reduce variability in the surgical rating, all surgeries are performed by a single surgeon at each institute.

The surgical rating scores (SRS) condition at 15-minute intervals will be recorded and rated by an anesthesiologist during the Procedures. In case of a sudden change in surgical conditions, additional scores are obtained. If conditions are poor (score 0 or 2), muscle relaxation is increased according to protocol.

Before commencing the study, both the surgeon and the anesthesiologists will receive training in how to use and implement the specific study Procedures and how to rate the surgical condition score.

Moreover, the first five Procedures performed in conformance with this protocol will not be used for data analysis; thus, the Procedures will be practiced five times before data collection starts.

Intubation score

At the end of intubation, the intubation condition is scored by anesthesiologist by using the same score of endolaryngeal surgical condition

Video images

The video images will be collected from the camera connected to endoscope placed

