Based on data from the BLISS study¹⁵, the proportion of patients a with a score of Excellent on the Surgical Rating Score (SRS) among subjects who receive deep NMB with Rocuronium is approximately 99%, while this proportion for patients who received moderate NMB with atacurium followed by mivacurium was lower (82%)..

By using 80% power and 1-sided $\alpha=0.05$, we performed sample size calculation by using the following formula.

For the proportion outcomes

$$n = \frac{2(\bar{p})(1 - \bar{p})(Z_{\beta} + Z_{\alpha})^2}{(p_1 - p_2)^2}$$

All expected primary outcome, secondary outcomes and calculated sample sizes are shown in the following table

	Deep NMB	Mode rate NMB	Sample size
Primary outcome			80% Power
- Proportion of Excellent	99%	82%	36/arm

Since we expect 13% of withdrawal from the study¹⁶, we need to inflate the total sample size to **80 subjects (40 subjects per arm)**.

As mentioned in the earlier session, the first five Procedures performed in conformance with this protocol will not be used for data analysis; thus, the Procedures will be practiced five times each center before data collection starts.

Therefore, the total enrolled patients are 110 patients.

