
2.9 Adverse Experience Reporting
	
All serious adverse experiences, regardless of relatedness to study medications will be collected throughout the course of study therapy and at least 7 days after the end of study therapy.
 
1. Recording Adverse Experiences
 
An adverse experience is defined as any unfavorable and unintended change in the structure, function, or chemistry of the body temporally associated with the use of the study's products, whether or not considered related to the use of the product. Any worsening (i.e., any clinically significant adverse change in frequency and/or intensity) of a preexisting condition which is temporally associated with the use of the product, is also an adverse experience.
 
Changes resulting from normal growth and development which do not vary significantly in frequency or severity from expected levels are not to be considered adverse experiences. Examples of this may include, but are not limited to, teething, typical crying in infants and children, and onset of menses or menopause occurring at a physiologically appropriate time.
 
Adverse experiences may occur in the course of the use of a product in clinical studies or within the follow-up period specified by the protocol, or prescribed in clinical practice, from overdose (whether accidental or intentional), from abuse, and from withdrawal.
 
Such events will be recorded at each examination on the Adverse Experience Case Report Forms/Worksheets.
 
2. Immediate Reporting of Adverse Experiences to the SPONSOR Serious Adverse Experiences
 
Any serious adverse experience, including death due to any cause, which occurs to any subject/subject entered into this study or within 14 days following cessation of treatment or within the established off therapy follow-up period for safety described in the protocol, whether or not related to the study product, must be reported within 24 hours to one of the individual(s) listed on the contact information page.
 
Additionally, any serious adverse experience considered by an investigator who is a qualified physician to be possibly, probably, or definitely related to the investigational product that is brought to the attention of the investigator at any time outside of the time period specified in the previous paragraph also must be reported immediately to one of the individuals listed on the sponsor contact information page found in the administrative binder. All subjects/subjects with serious adverse experiences must be followed up for outcome.
 
3. Responsibility for Reporting Adverse Experiences
 
All adverse experiences will be reported to regulatory agencies, IRB/IECs, in accordance with all applicable global laws and regulations.

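### The practice procedures (a planned 30 of 110 enrolled patients) are excluded from data analysis with no exception for safety, which conflicts with the adverse-experience rules in section 2.9

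*Combined protocol and SAP*

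**What the plan says.** Under Surgical rating in section 2.7, after a paragraph on training the raters, the plan states that "the first five Procedures performed in conformance with this protocol will not be used for data analysis". The Sample size calculation in the same section repeats the sentence, adds that "the Procedures will be practiced five times each center before data collection starts", and ends: "Therefore, the total enrolled patients are 110 patients". The synopsis gives the number of centres: "This study will be conducted at 6 centers throughout Thailand".

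Neither place limits the exclusion to efficacy or to the surgical score.

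On safety, the plan says the following:

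- **Synopsis, Safety Analysis.** It refers to post-marketing reporting practice ("Responsibility for clinical follow-up resides with the prescribing physician"). It defines no safety population, denominator or adverse-event table.
- **Section 2.7, Other outcomes.** The proportion of patients with residual block is an outcome at named times in the operating room and the PACU.
- **Section 2.7, Additional variables and the follow-up paragraphs after it.** The incidence of bradycardia and hypotension is recorded. Desaturation, reintubation, aspiration pneumonia, hospital death, and nausea or vomiting are also assessed.
- **Section 2.9.** "All serious adverse experiences, regardless of relatedness to study medications will be collected throughout the course of study therapy" and for at least a week afterwards. Adverse experiences go on dedicated CRF pages at each examination, and the 24-hour report covers any subject entered into the study.

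**The concern.** The practice patients are enrolled, treated to the protocol and counted in the 110. The stated purpose of the practice cases is to rehearse the procedures before data collection. That is a reason to set aside their surgical ratings. It is not a reason to set aside what happened to them after they received study rocuronium and sugammadex.

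Two things are at stake. First, any safety summary that follows the text would describe only part of the treated population, and a reader of the report could not tell what happened in each centre's first cases. Second, site staff face two instructions that do not fit together: these cases come before data collection, yet adverse experiences must be recorded on CRFs and serious ones reported for every subject entered.

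**Working it through.** **Inputs**

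- Practice procedures: 5 per centre (2.7, Sample size calculation). The Surgical rating text alone does not say per centre.
- Centres: 6 (synopsis, Study Design).
- Patients for analysis: 80, or 40 per arm, taken as the plan states it.
- Total enrolled: 110 (2.7, Sample size calculation).
- Appended results table: 48 moderate and 49 deep.

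**1. The plan's own total.** 5 x 6 = 30, and 80 + 30 = 110. This reproduces the stated figure exactly and confirms the per-centre reading.

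**2. Planned share excluded.** 30/110 = 27.3%.

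**3. Share at the numbers in the appended table.** 48 + 49 = 97, which fits neither 80 nor 110. If 30 practice patients came on top of the 97, the share is 30/127 = 23.6%. If enrolment stopped at 110, at most 110 - 97 = 13 patients were left out, or 11.8%. In the same table, nausea or vomiting in the deep group is 4 (8.2%) = 4/49, the denominator also used for surgical grading. No separate safety set is visible.

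**4. Effect on precision with zero events.** The one-sided 95% upper bound is 1 - 0.05^(1/n).

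- n = 80: 3.7%
- n = 110: 2.7%

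Both pool the arms and assume that every enrolled patient is treated.

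**5. Chance of at least one event.** This is 1 - (1 - r)^n. The documents give no event rate, so r is assumed and shown over a range.

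| Assumed rate r | n = 80 | n = 110 | the 30 practice cases alone |
|---|---|---|---|
| 1% | 55% | 67% | 26% |
| 2% | 80% | 89% | 45% |
| 3% | 91% | 96% | 60% |

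The last column is the chance that an event occurs among the practice cases. It is not the chance that the event is lost, because a serious one is still reportable under 2.9.

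**6. The passages side by side.** Section 2.7 puts the practice cases before data collection and outside data analysis. Section 2.9 requires CRF recording of adverse experiences and has no exception for practice cases. For an enrolled, treated patient, both cannot be followed literally.

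**The case against.** The exclusion appears only under surgical rating and sample size. The Safety Analysis paragraph and section 2.9 do not repeat it, so the intention may have been rating consistency only. Most of the safety variables have no specified analysis for any patient: of those listed, only residual block is a named outcome with a planned comparison. The synopsis counts everyone entered into CRFs in the enrollment population and leaves exclusions to a later Data Analysis Plan. These points stand, and they limit the size of the finding. They do not remove it, because the exclusion is worded without limit in both places and nothing restores the practice cases.

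A reader might go further and infer any of the following, which the documents do not support:

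- **That 27% of exposed patients drop out of every safety rate.** The plan defines no set of safety rates, so this reads more into the text than it says. The 27% is also a planned share.
- **That serious events in practice cases go unreported.** Section 2.9 covers any subject entered.
- **That the omission biases reported rates downward.** The documents give no evidence of a higher event rate in practice cases. They describe marketed drugs and prior training.
- **That a trial conclusion about safe discharge rests on a selected subset.** The sentence on safe discharge in section 2.2 is rationale, and it is tied to discharge-readiness criteria, not to adverse events.

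**Conclusion.** The point holds in a limited form. As written, section 2.7 leaves 30 of a planned 110 enrolled and treated patients out of the residual-block proportions and out of any summary of the other safety variables. Its placing of these cases before data collection conflicts with section 2.9. The statistical gain from correcting this is modest: one percentage point on the zero-event upper bound (3.7% to 2.7%). The main benefit is a complete account of treated patients.

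This rests on the per-centre reading, which the total of 110 confirms, and on all enrolled patients being treated. The documents do not say whether practice cases are randomised. Their split by arm is therefore unknown, and they cannot support a between-arm comparison. The 97 patients in the appended table make an account of the practice cases more necessary, but do not show how many were omitted.

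**What to change.** - **Section 2.7, Surgical rating and Sample size calculation.** Limit the exclusion of the first five procedures per centre to the efficacy analysis, including discharge readiness. Replace the clause placing them before data collection with wording consistent with section 2.9, so that safety variables and adverse experiences are recorded for them. Changing only the analysis clause would leave the conflict in place.
- **Safety Analysis.** Define the safety population as all enrolled patients who received study rocuronium or sugammadex. Summarise adverse experiences, serious adverse experiences, the safety events listed in section 2.7 and residual block descriptively, by block depth given. Show practice cases in a separate column and in the total.
- **Comparisons.** Keep all between-arm tests, including any on residual block, on the randomised post-practice patients. State whether practice cases are randomised.

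The cost is safety CRF pages for about 30 patients who are already enrolled and monitored, plus one table column. Pooled rates mix practice and trial-phase patients, which the separate column makes visible. If the data have already been analysed, the same table can be added at reporting, provided that records of the practice cases were kept. The primary comparison is unaffected.

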- 1) The proportion of patients who are ready to be discharged from post-operative care, defined as Modified Aldrete's score ≥ 9 , at arrival, 15,30,60, 90 minutes after reach of TOF > 0.9 will be summarized.
- 2) The proportion of patients who are ready to be discharged from the operating room, defined as TOF > 0.9 at time of tracheal extubation, at 1,3,5, 10 minutes after finish of Procedures will be summarized.
- 3) The frequency of patients with clinical signs of early recovery during Endolaryngeal Procedures will be compared between the deep NMB and Moderate NMB arms using Fisher's Exact test.

Clinical signs of early recovery:

- 1) Airway pressure alarm
- 2) Movement of Vocal cords on Laryngeal Video monitor
- 3) Movement of the abdomen
- 4) Change of End Tidal CO₂

Other outcomes:

-

- 1) Proportion of patient at risk of Post-Operative Residual Curarization (PORC) (PORC) (TOF ratio < 0.9) at 1,3,5,10, minutes after finish of Procedures and at arrival ,15,30, 60,90minutes during Post-Operative Care Unit stay.
- 2) Time to ready-to-discharge from Post-operative Care Unit which is time from Post-operative Care Unit (PACU) admission to reach "acceptable" score of Post-operative discharge score.
- 3) Time to ready-to-discharge from operating room, which is time from finish of Procedures to train of Four ratio > 0.9
- 4) Intubating condition in patients who has endotracheal insertion. This will be assessed by anesthesiologist right after finishing intubation by using the same score of endolaryngeal surgical condition

Categorical variables will be compared using the Fisher's exact test while continuous variables will be compared using the student's t-test or Mann-Whitney U test, depending on the sample distribution.

Descriptive will be utilized to describe surgical conditions rating by Anesthesiologists during the Procedures, and VDO Surgical condition scoring by an ENT surgeon and Anesthesiologist. Categorical variables will be summarized by frequency and percent while continuous variables will be summarized by the mean, median, standard deviation, and range.

Descriptive and univariate statistics may be utilized to describe demographics and baseline characteristics of subjects. Multivariate logistic regression analysis may be employed to examine the predictive value of various baseline factors on efficacy endpoints.

Sample size calculation:

The primary outcome's sample size calculation:

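### With about 7 to 8 non-excellent patients expected, the optional logistic regression on the primary endpoint would be overfitted, and a treatment-arm term would probably have no finite estimate

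*Combined protocol and SAP*

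**What the plan says.** Section 2.7, Statistical Methods, closes its list of analyses with one sentence on modelling: "Multivariate logistic regression analysis may be employed", and the stated purpose is "to examine the predictive value of various baseline factors on efficacy endpoints". The section does not list the baseline factors, cap the size of the model, say whether treatment arm is a term, or say what happens if a cell is empty. The software is to be STATA or SPSS, depending on availability.

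The primary endpoint is binary: a surgical conditions score of excellent (total 8 to 9) or not. It is compared between arms by Fisher's exact test. The sample size calculation in the same section assumes 99% excellent in the deep arm and 82% in the moderate arm. It is introduced by "By using 80% power and 1-sided" alpha of 0.05, and reaches 36 per arm, raised to 40 for withdrawal. No rates are given for the other efficacy endpoints.

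**The concern.** What a logistic model can support depends on the size of the smaller outcome group, here the patients who are not excellent. The plan expects that group to be very small and almost wholly in one arm. Two problems follow, and they need to be kept apart.

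- **Overfitting.** An unrestricted set of factors fitted to a handful of failures gives wide intervals, exaggerated coefficients and chance predictors, even when the fit converges.
- **Separation.** If the deep arm has no failures and arm is in the model, the maximum-likelihood odds ratio for arm is infinite and its standard error cannot be used.

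At stake is the credibility of any adjusted effect or predictor reported from this model. The primary test is not at stake.

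**Working it through.** **Inputs** (Section 2.7 unless noted): excellent rates 99% and 82%; 36 per arm before and 40 after the allowance for withdrawal; six centres (synopsis); randomisation stratified by use of an endotracheal tube (Section 2.5).

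**1. The plan's sample size.** Mean rate = (0.99 + 0.82)/2 = 0.905. The plan's formula gives 2 × 0.905 × 0.095 × (0.842 + 1.645)² / 0.17² = 36.8, which rounds up to 37. A version with separate variances under the null and the alternative gives 36. The stated 36 is reproduced, so the rates below are those the plan used.

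**2. Expected failures on the primary endpoint.**
- 40 per arm: 40 × 0.01 + 40 × 0.18 = 0.4 + 7.2 = 7.6
- 36 per arm: 36 × 0.01 + 36 × 0.18 = 0.36 + 6.48 = 6.84

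The total is random: its central 90% range at 40 per arm is about 4 to 12. Two parameters leave 7.6/2 = 3.8 failures each; five leave 7.6/5 = 1.5.

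**3. Chance of no failure in the deep arm** = (true excellent rate)^n.

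| True deep-arm rate | 36 per arm | 40 per arm |
|---|---|---|
| 99.5% | 84% | 82% |
| 99% (plan) | 70% | 67% |
| 98% | 48% | 45% |
| 97% | 33% | 30% |

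At 40 per arm the chance drops below one half once the true rate is under 0.5^(1/40) = 98.3%.

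**4. Chance of separation for candidate models.** This was simulated with 1,500 trials per cell at the plan's rates, testing each data set for a finite maximum-likelihood solution by linear programming. The covariates are assumptions: all unrelated to outcome, two continuous, common binary factors at 40 to 50%, a rare binary factor at 10%, and six equal centres. Results at 40 per arm:

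| Factors in the model | Without arm | With arm |
|---|---|---|
| Age, BMI | 0% | 66% |
| + sex | 4% | 68% |
| + tube stratum | 7% | 68% |
| + two-level ASA | 10% | 68% |
| those five + one rare factor | 48% | 83% |
| those five + six centres | 85% | 94% |

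At 36 per arm, the five common factors separate in 14% of trials without arm and 73% with it.

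**5. Size of the distortion, and whether a penalised method removes it.** In a further simulation of five covariates plus arm, ordinary maximum likelihood gave runaway coefficients in about 63% of trials. The average estimate of a covariate effect with true value 0.5 was about 0.74 (estimates capped at 5). With Firth's penalty the figures were under 1% and 0.52. Without an arm term, ordinary maximum likelihood gave runaway coefficients in about 8% of trials.

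**The case against.** The best defence is that the sentence concerns baseline factors. Treatment arm is not one, and the plan promises no adjusted treatment effect. Without arm, a small model of common factors nearly always has a finite fit. This stands, and it rules out a reading that the regression will usually break down as written: that needs an arm term, or many or sparse factors. Even with arm included and the deep arm empty, it is the arm coefficient that diverges; the other coefficients are still estimated, in effect from the moderate arm alone. What the defence does not remove is the overfitting. It also leaves open whether a factor expected to shift the outcome by 17 percentage points is in the model.

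Three further limits stand.

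- **Other endpoints.** A reader might extend the figures to early-recovery signs or readiness to discharge. The documents give no rates for these, so nothing can be said about them.
- **The results table at the end of the document.** It shows 0 of 49 deep-arm and 5 of 48 moderate-arm patients as not acceptable, which a reader might take as the predicted empty cell. That row counts good and excellent together (scores 6 to 9). A patient scoring 6 or 7 is acceptable there but a failure on the primary endpoint. The table gives no count of excellent scores.
- **The 99%.** The plan calls it approximate and takes it from a study of laparoscopic surgery, so the 67 to 70% should be read with the range in step 3.

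Finally, a model of arm plus stratum answers a different question from the plan's search for predictors. That is correct, and such a model should be labelled accordingly.

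**Conclusion.** The concern holds for the primary endpoint, and it is minor. About 7 to 8 failures cannot support an open list of factors in an ordinary logistic model. With arm included, the probability of no finite odds ratio for arm is about 67 to 70% on the plan's rates, and about 45% at 40 per arm if the true deep-arm rate is 98%. Without arm and with a few common factors, separation is about 0 to 10% at 40 per arm, and the problem is imprecision and exaggerated effects. These sizes rest on the 99% and 82% assumptions and, for the models with covariates, on the simulated covariates described.

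The analysis is optional, and Fisher's exact test handles an empty cell, so the trial's primary conclusion does not depend on this.

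**What to change.** In Section 2.7, Statistical Methods, for the primary endpoint:

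- Replace ordinary maximum-likelihood logistic regression with Firth-penalised (or exact) logistic regression. Limit the terms to treatment arm and the randomisation stratum (with or without endotracheal tube), and label the result a supportive adjusted treatment effect.
- Treat any analysis of other baseline factors as exploratory, one factor at a time, with the same penalised method.

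The cost is a sentence or two of text and a check that whichever of the two named packages is available can run the chosen method. The sample size, conduct and primary test do not change. What is lost is the open-ended multivariable search for predictors, which about 8 events cannot support.
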